Appendix 7. MANAGEMENT OF INFUSION RELATED REACTIONS, INCLUDING ALLERGIC REACTIONS OR ANAPHYLAXIS

In the event of infusion related reactions, Investigators should institute treatment measures according to best medical and nursing practice.

The following treatment guidelines should be employed:

If chills and fever (>100.4°F/38.0°C) occur, the infusion should be interrupted. Patients may be treated symptomatically (as described in [Section 5.5.2](#) Dose Delay) and the infusion should be restarted at 50% of the original rate.

Hypersensitivity reactions:

1. NCI-CTCAE Grade 1 allergic reaction:
 - Monitor for worsening condition. If the reaction worsens, stop the infusion. Institute premedication for subsequent infusions as per [Section 5.5.2](#) Dose Delay.
2. NCI-CTCAE Grade 2 allergic reaction:
 - Stop PF-06863135 infusion.
 - Administer bronchodilators, oxygen, acetaminophen, etc. as medically indicated.
 - Resume infusion at 50% of previous rate once reaction has decreased to Grade 1 in severity. Monitor closely for any worsening. If the reaction recurs, stop infusion. Institute premedication for subsequent infusions as per [Section 5.5.2](#) Dose Delay.
3. NCI-CTCAE Grade 3 or Grade 4 allergic reaction or anaphylaxis:
 - A Grade 3 anaphylaxis (hypersensitivity reaction) consists of symptomatic bronchospasm requiring parenteral medications with or without urticaria, allergy-related edema/angioedema, or hypotension.
 - A Grade 4 anaphylaxis (hypersensitivity reaction) is a life-threatening event requiring urgent intervention.
4. Treatment of Grade 3 or Grade 4 allergic reaction or anaphylaxis:
 - Stop the PF-06863135 infusion immediately and disconnect infusion tubing from the patient.
 - Administer epinephrine, bronchodilators, antihistamines, glucocorticoids, intravenous fluids, vasopressor agents, oxygen, etc. as medically indicated.

PF-06863135

C1071001

Final Protocol Amendment 9, 28 March 2023

- Telephone Sponsor or designated representative to report an SAE as per [Section 8](#) Adverse Event Reporting.
- For a NCI-CTCAE Grade 3 or 4 hypersensitivity reaction, study treatment will be discontinued.

5. Re-treatment following Grade 1 or Grade 2 allergic reactions:

- Once the PF-06863135 infusion rate has been decreased due to an allergic reaction or cytokine release syndrome, it will remain decreased for all subsequent infusions.
- If the patient has a second reaction at the lower infusion rate, the infusion should be stopped and the patient should receive no further PF-06863135.
- If the patient experiences a Grade 3 or 4 allergic reaction or anaphylaxis at any time, the patient should receive no further PF-06863135.
- If there are questions concerning whether an observed reaction is consistent with an allergic reaction, cytokine release syndrome, or anaphylaxis, the medical monitor should be contacted immediately to assist with grading the reaction.

PK, pharmacodynamic and ADA sampling should continue as long as the sampling does not interfere with the medical treatment of the patient.

PF-06863135

C1071001

Final Protocol Amendment 9, 28 March 2023

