5.5.2. Dose Delays

Re-treatment following treatment interruption for treatment-related toxicity or at the start of any new cycle should not occur until all of the following parameters have been met:

- ANC $\geq 1,000/\text{mm}^3$ for PF-06863135, dexamethasone, and lenalidomide; $\geq 500/\text{mm}^3$ for pomalidomide;
- Platelets count $\geq 25,000/\text{mm}^3$ for PF-06863135 and dexamethasone; $\geq 30,000/\text{mm}^3$ for lenalidomide; $\geq 50,000/\text{mm}^3$ for pomalidomide;
- Non-hematologic toxicities have returned to baseline or Grade ≤ 1 severity (or, at the investigator's discretion, Grade ≤ 2 if not considered a safety risk for the patient).
- Recovery of treatment-emergent peripheral neuropathy to Grade ≤ 1 severity.

If a treatment delay results from worsening of hematologic or biochemical parameters, the frequency of relevant blood tests should be increased as clinically indicated.

If these conditions are met within 3 weeks of treatment interruption or cycle delay, study treatment may be resumed. Refer to the Dose Reductions Section 5.5.3 for adverse events requiring dose reduction at the time of treatment resumption.

If these conditions are not met, treatment resumption must be delayed up to a maximum of 3 weeks. If patients require discontinuation of study treatment for more than 42 days of Day 1 of the current cycle, then study treatment should be permanently discontinued, unless the investigator's benefit/risk assessment suggests otherwise after discussion with the Sponsor's medical monitor.

If a treatment interruption continues beyond the last day of the current cycle, then the day when treatment is restarted will be counted as Day 1 of the next cycle.

Recommended guidelines for dose delays of PF-06863135 for participants who have active [confirmed (positive by regulatory authority-approved test) or presumed (test pending/clinical suspicion)] SARS-CoV2 infection can be found in [Appendix 10](#).

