5.9.7. Infusion Related Reactions (IRR)

Following the first infusion of some monoclonal antibody therapeutics, some patients experience fever, headache, nausea, vomiting or hypotension. These adverse events (AEs) are generally ascribed to lysis of cellular targets, cytokine release, or complement activation.

Infusion related reaction is characterized by fever and chills, and less commonly hypotension, either experienced by a particular patient or if seen in other patients, pretreatment medication should be administered to reduce the incidence and severity. A regimen is suggested here; however, if local standard of care is a different regimen, this will be allowed. In cases of infusion reactions, patients should be pretreated with acetaminophen and diphenhydramine (or other antihistamine) approximately 0.5 to 2 hours before investigational product administration. The pretreatment medications will not be supplied by Pfizer. Suggested starting doses are 650 to 1000 mg acetaminophen and 50 mg diphenhydramine (or equivalent for other antihistamines) either IV or oral. Two (2) additional doses of acetaminophen may be administered approximately every 4-6 hours after the initial pretreatment or as needed.

PF-06863135
 C1071001
Final Protocol Amendment 9, 28 March 2023

Detailed guidance on treatment, dose interruptions and potential retreatment is provided in [Appendix 7](#).

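### Protocol Appendix 7: items 2 and 5 conflict on their natural reading for a Grade 2 allergic reaction recurring at the halved infusion rate, and three references to Section 5.5.2 lead to the wrong section

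*Protocol*

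**What the plan says.** Appendix 7 is the controlling text: Protocol Sections 5.9.7 (infusion related reactions) and 5.9.9 (hypersensitivity) both send the reader there for detail on handling and re-treatment.

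- **Item 2, Grade 2 allergic reaction.** Stop the infusion and treat. Then "Resume infusion at 50% of previous rate once reaction has decreased to Grade 1 in severity". Next comes "If the reaction recurs, stop infusion. Institute premedication for subsequent infusions as per" Section 5.5.2.
- **Item 5**, headed "Re-treatment following Grade 1 or Grade 2 allergic reactions". Once the rate has been lowered, "it will remain decreased for all subsequent infusions". Then: "If the patient has a second reaction at the lower infusion rate, the infusion should be stopped and the patient should receive no further" PF-06863135.
- **References to Section 5.5.2.** Appendix 7 cites that section three times: for symptomatic treatment of chills and fever, and for premedication in items 1 and 2.
- **Section 5.5.2 itself** is the dose-delay section. It opens "Re-treatment following treatment interruption for treatment-related toxicity or at the start of any new cycle should not occur until" a list of recovery criteria is met.
- **Section 5.9.7** holds the premedication text for infusion reactions: "patients should be pretreated with acetaminophen and diphenhydramine (or other antihistamine").

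**The concern.** Item 2 restarts the infusion at half rate, so the recurrence it describes happens at the reduced rate. Its next sentence arranges premedication for later infusions, which makes sense only if treatment goes on. Item 5 covers the same patients and ends treatment on a second reaction at the reduced rate. A site that follows item 2 can continue the drug, while a site that follows item 5 must stop it for good. The event and the appendix are the same in both cases.

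The stake is first of all consistent safety management of the individual patient. If such events occurred, they would also feed the tables of treatment discontinuation (SAP 8.2.3.3) and duration of treatment (SAP 8.2.2.12), with a result that depended on which line the site had read.

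The reference error adds to this. An investigator who looks up premedication during a reaction is sent to laboratory recovery thresholds.

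**Working it through.** No arithmetic underlies the conflict, so the check sets the texts side by side.

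**Step 1: follow one event through both items.** Take a patient with a Grade 2 allergic reaction at full rate. The infusion is stopped, the reaction settles to Grade 1, the infusion resumes at 50% of the previous rate, and the reaction returns.

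| Question | Item 2 | Item 5 |
|---|---|---|
| Is this patient covered? | Yes, Grade 2 allergic reaction | Yes, Grade 1 or 2 allergic reaction |
| Is this event covered? | Yes, a recurrence after the half-rate restart | Yes, if the full-rate reaction counts as the first and this as the second |
| This infusion | Stop | Stop |
| Later infusions | Given, with premedication | None |

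The items agree on the current infusion and disagree on every later one.

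**Step 2: look for text that settles it.** Section 5.9.7 refers back to Appendix 7. Section 5.9.9 says only that infusions may be stopped, and then also refers back. The instruction in Appendix 7 to call the medical monitor concerns what kind of reaction it is and its grade, not which re-treatment rule applies. Nothing resolves the question.

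**Step 3: find the limits of the conflict.** Item 1 (Grade 1) does not itself lower the rate. For Grade 3 or 4, items 4 and 5 agree that treatment ends. The chills-and-fever paragraph restarts at half rate but has no recurrence rule. The conflict is therefore confined to Grade 2 allergic reactions.

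**Step 4: check the references.** Section 5.5.2 contains neutrophil and platelet thresholds, recovery criteria for non-hematologic toxicity and neuropathy, the 3-week and 42-day limits, and a pointer for SARS-CoV2. It has no premedication and no symptomatic treatment of reactions, so all three references fail. Premedication appears in two other places. Section 5.9.7 covers infusion reactions. Section 5.9.1 covers cytokine release prophylaxis for the priming and first full doses. The two lists differ (only 5.9.1 includes dexamethasone), so a reader has to be told which one is meant.

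**Step 5: bound the reach.** Protocol Section 1.2.3.1 gives enrollment at the 22 June 2022 cutoff as 23 (Part 1 IV) + 30 + 20 + 15 + 4 + 9 = 101. Parts 1 SC, 1.1 and 2A are labelled SC there, and Parts 1C and 1D use fixed doses tied to the SC recommended dose (Section 3.1.1.4). At most 23 of 101 patients, about 23%, could ever have come under this text.

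**The case against.** The strongest reply is that the two items can be read together. There are three ways to do so:

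1. Item 2 governs the infusion in progress, and item 5 governs later ones. Item 5's heading on re-treatment and its rule on the rate of later infusions support this.
2. A second reaction at the lower rate means two reactions at that rate, so the first half-rate recurrence falls under item 2 alone.
3. The premedication sentence is separate from the recurrence sentence and applies to any Grade 2 reaction. The same instruction closes item 1.

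Each reading is possible, and so the text cannot be called flatly contradictory on every reading. But they do not agree with one another. The first two let treatment continue after the first half-rate recurrence. The third, taken alone, leaves item 5 to end it. The text does not choose between them, and in item 2 the premedication sentence directly follows the words on recurrence.

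The reply also stands on scope and impact. The selected dose is subcutaneous (Section 3.4) and enrollment is complete (Section 3.1). Appendix 7 calls itself guidance and defers to best practice. The infusion-reaction premedication regimen exists and is not hard to find. Against that, Section 5.4.1 still carries IV instructions, and Section 3.1 allows treatment up to about 30 months after the last patient's first dose.

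**Conclusion.** The point holds as a limited inconsistency in wording. For a Grade 2 allergic reaction that recurs after a half-rate restart, items 2 and 5 conflict on their natural reading and are otherwise ambiguous. This rests on two assumptions: that the premedication sentence belongs to the recurrence before it, and that the full-rate reaction counts as the first. The reference error needs neither assumption and is certain at all three places.

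A reader might infer more, and the documents do not support it:

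- That Appendix 7 gives opposite orders for infusion reactions in general. The conflicting lines cover only Grade 2 allergic reactions.
- That discontinuation counts or time on treatment have been distorted. No document reports such a recurrence, and no primary endpoint is shown to be affected.
- That the protocol lacks a premedication regimen for infusion reactions. Section 5.9.7 has one.

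The reach is at most 23 patients, and the number still on IV dosing is not given. For any one affected patient the difference is continued treatment against permanent discontinuation. It is a minor point overall, but it concerns stopping the drug and is easy to repair.

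**What to change.** - Reconcile Appendix 7 items 2 and 5 so that a single instruction covers a Grade 2 allergic reaction recurring at the reduced rate. State whether item 5 applies within the same infusion, to later infusions, or to both, and which event counts as the second reaction. The choice is a clinical one for the sponsor and investigators.
- Correct all three references to Section 5.5.2. For items 1 and 2, the infusion-reaction premedication text is in Section 5.9.7. For symptomatic treatment of chills and fever, the sponsor should name the section intended, since 5.9.7 itself refers back to Appendix 7 for treatment detail.

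The cost is a few lines in the next amendment or an administrative change letter. No analysis, sample size or SAP text changes.

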Appendix 8. DETAILED DOSE ESCALATION/DE-ESCALATION SCHEME FOR mTPI DESIGN

| Number of Patients Having DLT | Number of Patients Treated at a Dose Level | | | | | | | | | | |
|-------------------------------|--|-----|-----|-----|-----|-----|-----|-----|------|------|------|
| | n=2 | n=3 | n=4 | n=5 | n=6 | n=7 | n=8 | n=9 | n=10 | n=11 | n=12 |
| 0 | E | E | E | E | E | E | E | E | E | E | E |
| 1 | S | S | S | E | E | E | E | E | E | E | E |
| 2 | U | D | D | S | S | S | S | S | S | S | E |
| 3 | | U | U | U | D | S | S | S | S | S | S |
| 4 | | | U | U | U | U | D | S | S | S | S |
| 5 | | | | U | U | U | U | U | U | D | S |
| 6 | | | | | U | U | U | U | U | U | U |

E = Escalate to the next higher dose

S = Stay at the current dose

D = De-escalate to a lower dose

U = The dose is Unacceptably toxic

MTD/MAD = The highest dose yields the probability of DLT within the equivalence interval (20%, 30%).

Escalation/De-escalation algorithms for total number of patients treated at the current dose level (current and previous cohorts):

- With 1 patient treated at current dose level:
 - 0 DLT -> escalate;
 - 1 DLT or other toxicities occur (ie, those that have the potential to be DLTs if more severe) -> may add additional patients to assess safety on a cohort size of n=2-4.
- With 2 patients treated at current dose level:
 - 0 DLT -> escalate;
 - 1 DLT -> remain at the same dose;
 - 2 DLTs -> de-escalate and consider current dose as intolerable.
- With 3 patients treated at current dose level:
 - 0 DLT -> escalate;
 - 1 DLT -> remain at the same dose;
 - 2 DLTs -> de-escalate;

PF-06863135

C1071001

Final Protocol Amendment 9, 28 March 2023

- 3 DLTs -> de-escalate and consider current dose as intolerable.
- With 4 patients treated at current dose level:
 - 0 DLT -> escalate;
 - 1 DLTs -> remain at the same dose;
 - 2 DLTs -> de-escalate;
 - 3-4 DLTs -> de-escalate and consider current dose as intolerable.
- With 5 patients treated at current dose level:
 - 0 or 1 DLT -> escalate;
 - 2 DLTs -> remain at the same dose;
 - 3-5 DLTs -> de-escalate and consider current dose as intolerable.
- With 6 patients treated at current dose level:
 - 0-1 DLT -> escalate;
 - 2 DLTs -> remain at the same dose;
 - 3 DLTs -> de-escalate;
 - 4-6 DLTs -> de-escalate and consider current dose as intolerable.
- With 7 patients treated at current dose level:
 - 0-1 DLT -> escalate;
 - 2-3 DLTs -> remain at the same dose;
 - 4-7 DLTs -> de-escalate and consider current dose as intolerable.
- With 8 patients treated at current dose level:
 - 0-1 DLT -> escalate;
 - 2-3 DLTs -> remain at the same dose;
 - 4 DLTs -> de-escalate;
 - 5-8 DLTs -> de-escalate and consider current dose as intolerable.

PF-06863135

C1071001

Final Protocol Amendment 9, 28 March 2023

[figure not shown]
- With 9 patients treated at current dose level:
 - 0-1 DLT -> escalate;
 - 2-4 DLTs -> remain at the same dose;
 - 5-9 DLTs -> de-escalate and consider current dose as intolerable.
- With 10 patients treated at current dose level:
 - 0-1 DLT -> escalate;
 - 2-4 DLTs -> remain at the same dose;
 - 5-10 DLTs -> de-escalate and consider current dose as intolerable.
- With 11 patients treated at current dose level:
 - 0-1 DLT -> escalate;
 - 2-4 DLTs -> remain at the same dose;
 - 5 DLTs -> de-escalate (mTPI suggests “remain at the same dose”);
 - 6-11 DLTs -> de-escalate and consider current dose as intolerable.
- With 12 patients treated at current dose level:
 - 0-2 DLTs -> escalate;
 - 3-5 DLTs -> remain at the same dose;
 - 6-12 DLTs -> de-escalate and consider current dose as intolerable.

PF-06863135

C1071001

Final Protocol Amendment 9, 28 March 2023

Appendix 9. SUBCUTANEOUS INJECTION SITE LOCATIONS

Injection site locations include a maximum of 8 unique administration sites distributed across 4 abdominal quadrants with a possibility of up to 2 injection locations per quadrant.

Location 1 is proximal to the umbilicus and Location 2 is distal to the umbilicus.

Administer the required number of injections in the following order:

1. Lower Left Quadrant Location 1;
2. Lower Right Quadrant Location 1;
3. Lower Left Quadrant Location 2;
4. Lower Right Quadrant Location 2;
5. Upper Right Quadrant Location 1;
6. Upper Left Quadrant Location 1;
7. Upper Right Quadrant Location 2;
8. Upper Left Quadrant Location 2.

Injections to the abdomen are preferred. If SC injections in the abdominal location are not possible, SC injections can be administered in a distributed manner in the thighs. SC injections in the upper extremities (eg, deltoid, upper and lower arm) are not permitted.

Track the patient's injection site(s) sequentially on this diagram with a red pen and mark the injection sites on the patient's abdomen according to your clinic's standard practice.

Record the location, time of each injection and any injection site reactions in the patient's source records and study CRF. Complete one CRF per injection

PF-06863135
 C1071001
Final Protocol Amendment 9, 28 March 2023

Appendix 10. Alternative Measures During Public Emergencies

The alternative study measures described in this section are to be followed during public emergencies, including the COVID-19 pandemic. This appendix applies for the duration of the COVID-19 pandemic in participating countries and will become effective for other public emergencies only upon written notification from Pfizer.

Use of these alternative study measures are expected to cease upon the return of business as usual circumstances (including the lifting of any quarantines and travel bans/advisories).

Eligibility

Regarding eligibility, while SARS-CoV2 testing is not mandated for this study you should follow local clinical practice standards for testing. If a participant has a positive test result for active SARS-CoV2 infection, is known to have asymptomatic infection or is suspected of having SARS-CoV2, he/she should be excluded at this time. Please note the protocol excludes patients with active infections:

Exclusion Criteria:

4. Patients with active uncontrolled bacterial, fungal or viral infection, including known human immunodeficiency virus (HIV) infection or acquired immunodeficiency syndrome (AIDS) related illness.

When the infection resolves, the patient could be considered for re-screening, if allowed by study protocol.

Telehealth Visits

In the event that in-clinic follow-up study visits cannot be conducted where sample collection is not performed or treatment not given, every effort should be made to follow up on the safety of study patients at scheduled visits per the [Schedule of Activities](#) or unscheduled visits. Telehealth visits may be used to continue to assess patient safety and collect data points. Telehealth includes the exchange of healthcare information and services via telecommunication technologies (eg, audio, video, video-conferencing software) remotely, allowing the participant and the investigator to communicate on aspects of clinical care, including medical advice, reminders, education, and safety monitoring. The following assessments must be performed during a telehealth visit

- Review and record study intervention(s), including compliance and missed doses.
- Review and record any AEs and SAEs since the last contact. Refer to [Section 8.1.4.2](#).
- Review and record any new concomitant medications or changes in concomitant medications since the last contact.

PF-06863135

C1071001

Final Protocol Amendment 9, 28 March 2023

- Review and record contraceptive method and results of pregnancy testing. Confirm that the patient is adhering to the contraception method(s) required in the protocol.

Study participants must be reminded to promptly notify site staff about any change in their health status.

Alternative Facilities for Safety Assessments

Laboratory Testing

If a study participant is unable to visit the site for protocol-specified safety laboratory evaluations, testing may be conducted at a local laboratory if permitted by local regulations. The local laboratory may be a standalone institution or within a hospital. The following safety laboratory evaluations as listed in [Table 11](#) may be performed at a local laboratory if necessary:

- Hematology;
- Blood chemistry;
- Coagulation;
- Urinalysis;
- Pregnancy test.

If a local laboratory is used, qualified study site personnel must order, receive, and review results. Site staff must collect the local laboratory reference ranges and certifications/accreditations for filing at the site. Laboratory test results are to be provided to the site staff as soon as possible. The local laboratory reports should be filed in the participant's source documents/medical records. Relevant data from the local laboratory report should be recorded on the CRF.

If a participant requiring pregnancy testing cannot visit a local laboratory for pregnancy testing, a home urine pregnancy testing kit with a sensitivity of at least 25 IU/mL may be used by the participant to perform the test at home, if compliant with local regulatory requirements. The pregnancy test outcome should be documented in the participant's source documents/medical records and relevant data recorded on the CRF. Confirm that the participant is adhering to the contraception method(s) required in the protocol.

Electrocardiograms

If the participant is unable to visit the study site for ECGs, the participant may visit an alternative facility to have the ECGs performed. Qualified study site personnel must order, receive, and review results.

PF-06863135
C1071001
Final Protocol Amendment 9, 28 March 2023

Study Intervention

If the safety of a trial participant is at risk because they cannot complete required evaluations or adhere to critical mitigation steps, then discontinuing that participant from study intervention must be considered.

Dose Delays

The following is recommended for the administration of PF-06863135 for participants who have active [confirmed (positive by regulatory authority-approved test) or presumed (test pending/clinical suspicion)] SARS-CoV2 infection:

- For symptomatic participants with active SARS-CoV2 infection, investigational treatment should be delayed for at least 14 days from the start of symptoms. This delay is intended to allow the resolution of symptoms of SARS-CoV2 infection.
- Prior to restarting treatment, the participant should be afebrile for 72 hours, and SARS-CoV2-related symptoms should have recovered to \leq Grade 1 for a minimum of 72 hours. Notify the study team when treatment is restarted.
- Continue to consider potential drug-drug interactions as described [Section 5.9](#) and [Appendix 11](#) for any concomitant medication administered for treatment of SARS-CoV2 infection.

Adverse Events and Serious Adverse Events

If a participant has COVID-19 during the study, this should be reported as an adverse event (AE) or serious adverse events (SAE) and appropriate medical intervention provided.

Temporary discontinuation of the study intervention may be medically appropriate until the participant has recovered from COVID-19.

It is recommended that the investigator discuss temporary or permanent discontinuation of study intervention with the study medical monitor.

PF-06863135

C1071001

Final Protocol Amendment 9, 28 March 2023

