1.2.3.1. Safety

The safety, efficacy, and PK of elranatamab were initially evaluated in Phase 1 study (C1071001) as monotherapy (IV and SC) or in combination with lenalidomide or pomalidomide.

As of the 22 June 2022 data cutoff date, 101 participants have been enrolled in the study as follows: 23 in Part 1 IV dose escalation, 30 in Part 1 SC dose escalation, 20 in Part 1.1 SC priming dose cohorts, 15 in Part 2A: SC dose dose expansion, 4 in Part 1C: elranatamab + lenalidomide and 9 in Part 1D: elranatamab + pomalidomide. In Part 1.1, to mitigate the risk of CRS and ICANS, participants received a priming dose of 600 µg/kg elranatamab (equivalent to 44 mg) on Day 1 prior to the first full dose of 1000 µg/kg (equivalent to 76 mg) on Day 8. In Part 2A, in addition to the priming dose of elranatamab, participants received pre-medication with dexamethasone, acetaminophen and diphenhydramine prior to the first 2 doses, priming dose and first full dose respectively.

Based on the data from this study, 76 mg QW administered SC was selected as the RP2D of elranatamab for future studies. This section will focus on safety data from participants who received elranatamab monotherapy at the full 1000 µg/kg or 76 mg [QW or Q2W] dosing regimen (N=41) regardless of priming dose or premedication.

In the 41 participants who received elranatamab monotherapy at the full 1000 µg/kg or 76 mg [QW or Q2W] dosing regimen, the most common all causality TEAEs (frequency $\geq 20\%$) were CRS (87.8%), neutropenia (78.0%), anemia (63.4%), ISR (56.1%), thrombocytopenia and fatigue (each 48.8%), diarrhea, hypophosphatemia and lymphopenia (each 39.0%), decreased appetite and dry skin (each 36.6%), back pain (34.1%), nausea and hypomagnesaemia (each 31.7%), AST increased and leukopenia (each 26.8%), ALT increased, fall, hypokalemia, pyrexia, vomiting, pain in extremity and weight decreased (each 24.4%), arthralgia, cough, dyspnoea, headache and pneumonia (each 22.0%).

For additional information, refer to the single reference safety document (SRSD), which for this study is the Investigator's Brochure.

PF-06863135
C1071001
Final Protocol Amendment 9, 28 March 2023

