5.2. Patient Compliance

All doses of PF-06863135 will be administered by the appropriately designated study staff at the investigational site. Oral medications lenalidomide, pomalidomide, and dexamethasone, if applicable, will be taken by the patient either at the site or at home.

The site will complete required dosage Preparation Record located in the Investigational Product manual (IP manual). The use of the Preparation Record is preferred but it does not preclude the use of an existing appropriate clinical site documentation system. The existing clinical site's documentation system should capture all pertinent/required information on the

PF-06863135

C1071001

Final Protocol Amendment 9, 28 March 2023

preparation and administration of the dose. This may be used in place of the Preparation Record after approval from the sponsor and/or designee.

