7.1.1. Pregnancy Testing

For female patients of childbearing potential, a serum pregnancy test, with sensitivity of at least 25 mIU/mL, will be performed at screening and on Day 1 of each cycle.

A negative pregnancy test result is required before the patient may receive the investigational product. Pregnancy tests will also be done whenever 1 menstrual cycle is missed during the active treatment period (or when potential pregnancy is otherwise suspected). Pregnancy tests may also be repeated if requested by institutional review boards (IRBs)/ethics committees (ECs) or if required by local regulations.

In addition, for Parts 1C, 1D, 2C, and 2D, pregnancy testing should occur at C1D1 and weekly during first cycle, and if menstrual cycles are irregular should occur every 2 weeks thereafter. In addition, pregnancy prevention programs (PPP) for lenalidomide and pomalidomide must be followed.

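### Appendix 10 gives the fallback home pregnancy kit's sensitivity as 25 IU/mL where Section 7.1.1 has 25 mIU/mL: most likely a dropped 'm', a minor unit error that should be corrected

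*Protocol*

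**What the plan says.** For women who could become pregnant, Section 7.1.1 specifies the following: "a serum pregnancy test, with sensitivity of at least 25 mIU/mL, will be performed at screening and on Day 1 of each cycle". It makes a negative result a condition for receiving investigational product. For Parts 1C, 1D, 2C and 2D it adds weekly testing in the first cycle, and testing every two weeks after that if cycles are irregular. It also states that "pregnancy prevention programs (PPP) for lenalidomide and pomalidomide must be followed".

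Appendix 10 applies during the COVID-19 pandemic, and in other public emergencies once the sponsor gives written notice. It allows safety laboratory tests, including the pregnancy test, to be done at a local laboratory. One further fallback follows: "If a participant requiring pregnancy testing cannot visit a local laboratory for pregnancy testing", she may use a urine kit herself, and the wording on its limit and use is "sensitivity of at least 25 IU/mL may be used by the participant to perform the test at home, if compliant with local regulatory requirements". Outcomes are to be documented in the source records, with relevant data on the CRF.

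Section 5.2 bears on how far a home result could influence dosing. For elranatamab, "All doses of PF-06863135 will be administered by the appropriately designated study staff at the investigational site". The oral drugs (lenalidomide, pomalidomide, dexamethasone) "will be taken by the patient either at the site or at home".

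**The concern.** The two sections use the same number, 25, and nearly the same phrasing, but units that differ by a factor of 1000. Read literally, Appendix 10 would accept a kit that misses any pregnancy below 25,000 mIU/mL, while the routine test must detect 25 mIU/mL.

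The figure has a function. It is the only numeric specification for the home kit, and Section 7.1.1 ties dosing to a negative test. Section 5 classes lenalidomide and pomalidomide as investigational products, Sections 1.2.6 and 1.2.7 say that both can cause embryo-fetal toxicity, and both may be taken at home. A site that selected a kit from the literal wording could therefore rely on an uninformative negative result. The documents give no sign that this has happened.

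**Working it through.** This is a comparison of two stated specifications. Neither is derived from anything else, so there is no calculation in the plan to reproduce.

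**Inputs**
- Routine serum test, Section 7.1.1: 25 mIU/mL.
- Home urine kit, Appendix 10: 25 IU/mL.
- Conversion: 1 IU = 1000 mIU.
- Patients in the parts that give lenalidomide or pomalidomide, Section 1.2.3.1, at the 22 June 2022 cutoff: "4 in Part 1C: elranatamab + lenalidomide and 9 in Part 1D: elranatamab + pomalidomide", out of 101 enrolled.

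**Unit conversion**
- 25 IU/mL × 1000 mIU/IU = 25,000 mIU/mL.
- Ratio to the routine limit: 25,000 / 25 = 1000.
- With the 'm' restored: 25 / 25 = 1, so the two sections agree exactly.
- If the slip was IU/mL for IU/L, the corrected value is the same, because 25 IU/L = 25 mIU/mL.

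**Is a different limit intended?** One test uses serum and the other urine, so they are different assays. That does not account for a 1000-fold gap, and the protocol gives no rationale for a looser home limit. These are the only two pregnancy-test sensitivities in the protocol.

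**Direction of the error.** A kit that detects 25 mIU/mL also meets the literal requirement of 25 IU/mL or better. The error therefore excludes no adequate kit; it only fails to exclude inadequate ones.

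**Context count.** 4 + 9 = 13 patients in Parts 1C and 1D; 13 / 101 = 12.9%. This describes the size of the partner-drug parts and does not estimate who is exposed to the error. It counts both sexes, and the home-test provision covers any patient in any part who needs pregnancy testing. The documents do not say how many patients were women of childbearing potential or how many were tested at home.

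**The case against.** The strongest objection is that this is a typographical slip with almost no consequence. Several conditions must coincide before a home test is used: the emergency appendix is in force, and the patient can reach neither the site nor a local laboratory. The kit must also satisfy local rules. A patient attending for elranatamab is at the site anyway. For the partner drugs, the prevention programs apply, and footnotes to Schedules of Activities B and C require the investigator to review Day 1 safety laboratory results before each cycle. Appendix 10 itself says that discontinuation must be considered when a patient is at risk because required evaluations cannot be done. Enrollment is complete, and the 41 patients in the population PK summary (Section 1.2.9.4) were aged 47 to 82, which suggests few women of childbearing potential. All of this stands and is why the point is minor. It does not make the stated limit right. The documents also do not give the test sensitivity that the prevention programs require, so they cannot be shown to replace the figure.

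A second objection is that the missing letter could come from text extraction of the PDF and not from the protocol. That is possible but speculative: Section 7.1.1 came through with its 'm' intact. A look at the page settles it.

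A third objection concerns the remedy. Appendix 10 asks for the outcome and relevant data, not expressly for the kit's brand or sensitivity, so a retrospective check may not always be possible. This is fair and limits the side recommendation. It does not affect the correction.

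**Conclusion.** The home-kit sensitivity in Appendix 10 is wrong as written. It is 1000 times looser than the limit in Section 7.1.1, and no other text in the protocol corrects or justifies it. The conclusion rests on the printed page matching the text available here, and on the same number in both places indicating one intended standard. The severity is minor: the wording applies only in a narrow contingency with other safeguards in place, it affects no endpoint, sample size, decision rule or analysis, and no inadequate kit or harm is documented. The number of patients affected, if any, cannot be determined from the documents.

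**What to change.** In the home-testing sentence of Appendix 10, change the unit from IU/mL to mIU/mL, so that the kit limit matches the 25 mIU/mL of Section 7.1.1. Confirm the wording against the protocol page first. The change is one letter. It can go into the next amendment, which needs IRB/EC approval under Section 12.1, or into an administrative change letter if that route is acceptable; the amendment history shows such letters have been used before.

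Separately, search the CRF for pregnancy tests done at home. If there are none, nothing more is needed. If there are some, check the specification of each kit against 25 mIU/mL where the source records identify it, and note the cases where they do not.
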